## **6.5 METHODS OF ASSESSMENT**

### **6.5.1 Safety**

#### ***6.5.1.1 Clinical Laboratory Evaluations***

Local laboratories in the 9 centers will be used for this study for analysis of hematology, chemistry (including amylase), pregnancy testing, coagulation, cardiac biomarkers, serum free light chains, SPEP, 24-hour UPEP, SIFE, UIFE, urinalyses, and 24-hour urine protein excretion.

Hematology and chemistry results will be reviewed prior to dosing at each month's day 1 visit to confirm that continued dosing is appropriate.

#### ***6.5.1.2 Vital Signs***

Predose vital signs should be assessed within 30 minutes before dosing. Vital signs should be measured after the subject has been at rest 25 minutes. Within a single visit, assess in the same position for all time points.

Heart rate will be measured from the radial HR counted manually or with an automatic BP monitor over at least 15 seconds and adjusted per minute.

Blood pressure (systolic and diastolic) measurements should be taken from the same arm throughout the study using an automated BP monitor that uses an oscillometric method.

Respiratory rate will be measured over at least 15 seconds and adjusted per minute.

Body temperature can be measured using either oral or tympanic methods, but the method should be consistent throughout the study for a given subject.

#### **6.5.1.3 Physical Examination**

Any unfavorable changes in physical examination findings considered by the Investigator as clinically significant will be documented in the eCRF as an AE. Physical examinations must be performed by the Investigator or a medically qualified delegate.

A complete physical examination includes height (screening only), weight, and examination of the following: general appearance; head, ears, eyes, nose, and throat; neck; skin; cardiovascular system; respiratory system; gastrointestinal system; and nervous system. A directed physical examination includes weight and other components, which will be as clinically indicated. At all visits, the following are to be assessed: macroglossia, submandibular nodes/fullness, adenopathy, ecchymoses, liver/spleen size (palpable +/-), ascites (+/-), and edema (which should be quantified on a scale of 0-4+).

#### **6.5.2 Efficacy**

##### **6.5.2.1 Primary: Renal Response**

See Appendix 4.

##### **6.5.2.2 Secondary**

Comparisons of mGFR and eGFR at study entry.

Time to CKD 4 or 5

Time to eGFR < 15 or dialysis

Time to doubling of creatinine

Time to > 40% reduction in eGFR

Renal response and progression in patients who have had maintained hematologic responses at 26 months

Safety and tolerability of NEOD001

All cause mortality at 26 months

## **7 ADVERSE EVENTS/SERIOUS ADVERSE EVENTS AND REPORTING**

### **7.1 Adverse Events—Definition**

An AE is any untoward medical occurrence associated with the use of a drug in humans, whether or not considered drug related. An AE can, therefore, be any unfavorable and unintended sign (including a laboratory finding, for example), symptom, syndrome, or disease temporally associated with the use of a medicinal product, whether or not considered related to the medicinal product. Examples include:

- Any treatment-emergent signs and symptoms (events that are marked by a change from the subject's baseline/entry status [e.g., an increase in severity or frequency of preexisting abnormality or disorder])
- All reactions from study drug, abuse of drug, withdrawal phenomena, sensitivity, or toxicity to study drug

- Apparently unrelated illnesses
- Injury or accidents
- Exacerbations of the underlying disease (indication)
- Extensions or exacerbations or symptomatology, subjective events reported by the subject, new clinically significant abnormalities in clinical laboratory, physiological testing, or physical examination

The reporting period for AEs is from the time that the ICF is signed until the confirmatory EOS or the ETD visit or for 30 days after the last dose of study drug, whichever is later. All AEs, whether or not related to the study drug, must be fully and completely documented on the eCRF and in the subject's medical notes. The following attributes must be assigned: description, dates of onset and resolution, severity, assessment of relatedness to study drug (either related or not related), and action taken. The Investigator may be asked to provide additional follow-up information.

In the event that a subject is withdrawn from the study because of an AE, it must be recorded on the eCRF. The subject should be followed and treated by the Investigator until the AE has resolved, stabilized, or a new chronic baseline has been established.

The Investigator must report all AEs. At each visit the Investigator will ask the subject a nonspecific question (e.g., "Have you noticed anything different since your last visit?") to assess whether any AEs have been experienced since the last report or visit. Adverse events will be identified and documented on the eCRF in appropriate medical terminology. The severity and the relationship to the study drug will be determined and reported on the eCRF.

Note that any intermittent or as-needed ("PRN") use of medication (and specifically any newly prescribed medication) during the course of a study may indicate the occurrence of an AE that may need to be recorded on more than one eCRF.

## 7.2 Adverse Events—Severity Rating

Adverse events will be assessed according to NCI CTCAE version 4.0. Adverse events that do not have a corresponding CTCAE term will be assessed according to their impact on the participant's ability to perform daily activities as listed below. The severity of each AE should be characterized and then classified into one of five clearly defined categories as follows:

- **Grade 1 (mild):** Mild; asymptomatic or mild symptoms; clinical or diagnostic observations only; intervention not indicated.
- **Grade 2 (moderate):** Moderate; minimal, local or noninvasive intervention indicated; limiting age-appropriate instrumental activity of daily living (e.g., preparing meals, shopping for groceries or clothes, using the telephone, managing money).
- **Grade 3 (severe):** Severe or medically significant but not immediately life-threatening; hospitalization or prolongation of hospitalization indicated; disabling; limiting self-care activities of daily living (e.g., bathing, dressing and undressing, feeding self, using the toilet, taking medications, and not bedridden).
- **Grade 4 (life threatening):** Life-threatening consequences; urgent intervention indicated.
- **Grade 5 (fatal):** Death related to AE.

These five categories are based on the Investigator's clinical judgment, which in turn depends on consideration

of various factors such as the subject's reports, the Investigator's observations, and the Investigator's prior experience. The severity of the AE should be recorded in the appropriate section of the eCRF. The evaluation of severity is distinguished from the evaluation of "seriousness." A severe event might not meet the criteria for seriousness and a serious event might be evaluated as mild. For example, a subject might have a **severe** headache that does not require hospitalization and is consequently **not serious**; or a subject might have a **mild** myocardial infarction that requires hospitalization and is, therefore, **serious**.

### **7.3 Adverse Events—Causality Rating**

The causality of each adverse event should be assessed and classified by the Investigator as "related" or "not related." An event is considered related if there is "a reasonable possibility" that the event may have been caused by the product under investigation (i.e., there are facts, evidence, or arguments to suggest possible causation).

#### **Guidelines for "Related" Events**

- There is clear evidence to suggest a causal relationship, and other possible contributing factors can be ruled out.
- There is evidence to suggest a causal relationship, and the influence of other factors is unlikely.

There is some evidence to suggest a causal relationship (e.g., the event occurred within a reasonable time after administration of the study drug). However, the influence of other factors may have contributed to the event (e.g., the subject's clinical condition, other concomitant events).

#### **Guidelines for "Not related" Events**

- There is little evidence to suggest there is a causal relationship. There is another reasonable explanation for the event.
- An adverse event will be considered "not related" to the use of the product if any of the following tests are met:
  - An unreasonable temporal relationship between administration of the product and the onset on the AE (e.g., the event occurred either before, or too long after administration of the product for it to be considered product-related)
  - A causal relationship between the product and the AE is biologically implausible (e.g., death as a passenger in an automobile accident)
  - A clearly more likely alternative explanation for the AE is present (e.g., typical adverse reaction to a concomitant drug and/or typical disease-related event)

#### **Consider the Following When Assessing Causality**

- Temporal associations between the agent and the event
- Cessation or rechallenge
- Compatibility with known class effect
- Known effects of concomitant medications
- Preexisting risk factors
- A plausible mechanism

- Concurrent illnesses

#### **7.4 Serious Adverse Events and Unexpected Adverse events**

In addition to the severity rating, each AE is to be classified by the Investigator as "serious" or "not serious." The seriousness of an event is defined according to the applicable regulations and generally refers to the outcome of an event. An SAE is one that meets one or more of the following:

- Is fatal
- Is life-threatening
- Is persistent or significantly incapacitating or causes substantial disruption of the ability to conduct normal life functions
- Requires inpatient hospitalization
- Prolongs existing hospitalization
- Is a congenital anomaly or birth defect
- Is an important medical event that may jeopardize the subject and/or may require medical or surgical intervention to prevent one of the outcomes listed above

#### **Definition of Life-threatening**

An adverse event or suspected adverse reaction is considered "life-threatening" if, in the view of either the Investigator or Sponsor (and/or designee), its occurrence places the subject at immediate risk of death. It does not include an adverse event or suspected adverse reaction that, had it occurred in a more severe form, might have caused death.

#### **Definition of Hospitalization**

Hospitalization is defined by the Sponsor as a full admission to the hospital for diagnosis and treatment. This includes prolongation of an existing inpatient hospitalization.

Examples of visits to a hospital facility that do not meet the serious criteria for hospitalization include:

- Emergency room visits (that do not result in a full hospital admission)
- Outpatient surgery
- Preplanned or elective procedures
- Protocol procedures

The above events would not be reported as SAEs unless the event triggering the hospital visit is an SAE as defined by other SAE criteria such as life-threatening, results in persistent or significant disability/incapacity or as per medical judgment of the Investigator.

Any other event fulfilling the definition of serious that develops as a result of the in-hospital procedure or extends the hospital stay is an SAE.

## **Definition of Disability**

Disability is defined as a persistent and substantial disruption in a person's ability to conduct normal life functions.

## **Definition of Medically Significant**

Important medical events (medically significant events) that may not result in death, be life-threatening or require hospitalization may be considered to be an SAE when, based upon appropriate medical judgment, they may jeopardize the subject and/or may require medical or surgical intervention to prevent one of the outcomes listed in this definition. Examples of such events are a new diagnosis of cancer, intensive treatment in an emergency room or at home for allergic bronchospasm, or convulsions that do not result in hospitalization, or development of drug dependency or drug abuse.

An SAE may also include any other event that the Investigator or medical monitor judges to be serious, or that suggests a significant hazard, contraindication, side effect, or precaution.

## **Definition of Suspected Adverse Reactions**

Suspected adverse reaction is considered any AE for which there is a reasonable possibility that the drug caused the AE.

## **Definition of Unexpected**

An AE or suspected adverse reaction is considered "unexpected" if it is not listed in the Investigator Brochure or is not listed at the specificity or severity that has been observed. "Unexpected," as used in this definition, also refers to adverse events or suspected adverse reactions that are mentioned in the Investigator Brochure as occurring with a class of drugs or as anticipated from the pharmacological properties of the drug, but are not specifically mentioned as occurring with the particular drug under investigation.

### **7.4.1 Elective Procedures and Surgeries**

For the purposes of this protocol, the following conventions will apply for SAE reporting of elective procedures, and surgeries:

- A prescheduled elective procedure or a routinely scheduled treatment is not to be considered an SAE, even if the subject is hospitalized, provided the site stipulates that:
  - The condition requiring the prescheduled elective procedure or routinely scheduled treatment was present before and did not worsen or progress between the subject's consent to participate in the clinical trial and the time of the procedure or treatment
  - The prescheduled elective procedure or routinely scheduled treatment is the sole reason for admission and intervention.

An untoward medical event occurring during the prescheduled elective procedure or routinely scheduled treatment should be recorded as an AE or a SAE. Any concurrent medications should also be recorded on the eCRF.

### **7.4.2 Other Reportable Information**

In addition, and for the purposes of monitoring, any occurrence of exposure through lactation and any

pregnancy (with or without an AE) of a female subject or partner of a male subject should be reported, regardless of seriousness, according to the directions in Section 7.4.4. Any subject who becomes pregnant during the study must be withdrawn from study drug treatment, and will be followed to term.

#### **7.4.3 Disease Progression and Death**

Disease progression (including progression of hematologic condition and/or organ dysfunction of AL amyloidosis, and death due to disease progression) is generally recorded as part of the efficacy evaluation and should not be reported as a specific AE or SAE term. When an AE resulting from disease progression meets the requirements to be considered serious, the SAE verbatim term should be reported as the diagnosis that best describes the event rather than as “disease progression.” For instance, a subject with pleural effusion presents with shortness of breath. The cause of the shortness of breath is a pleural effusion resulting from disease progression. The event term may be reported as “pleural effusion” instead of disease progression.

Death should not be reported as an SAE term, but as a clinical outcome of a specific SAE. The cause of death, reported on a source document such as the Death Certificate or autopsy report, should be used as the event term for the SAE. For example, in a subject with acute heart failure that results in death, the SAE is reported as “acute heart failure” with an outcome of “death.”

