### **3.2 Endpoints**

#### **3.2.1 Primary Efficacy**

- Confirmed renal response rate after 12 months of treatment with NEOD001 or placebo (Appendix 1, Palladini 2014)

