#### **8.4 Analysis of Safety Endpoints**

Study drug administration data will be listed by study site, subject number, and visit; and any dose modifications will be flagged. Means and standard deviations will be used to summarize the total number of infusions per patient, the total dose of NEOD001 received per patient, and the number of patients whose infusions were interrupted for infusion reactions.

Safety and tolerability of NEOD001 will be assessed by vital signs, duration of therapy, routine laboratory assessments, frequency and severity of AEs as assessed by CTCAE grade. We will apply descriptive statistical methods to the data, supplemented by calculation of confidence intervals if indicated. We will also display the grades and patterns of adverse events within both treatment groups.

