**The most common side effects seen in ≥ 10% of the NEOD001-001 (Phase 1/2) subjects include:**

- Increased creatinine in blood
- Dizziness
- Cough
- Constipation
- Headache
- Vomiting
- Difficulty breathing (Dyspnea)
- Pain in hands and legs (pain in extremity)
- Back pain
- Muscle spasms
- Rash
- Urinary tract infection

Twenty three subjects were enrolled in the Phase 2 study and 129 subjects were enrolled in the Phase 3 study and received 24 mg/kg NEOD001 or placebo; the patients did not know what they were receiving. In the Phase 2 study, one subject experienced vasovagal syncope (fainting) but recovered from it.

Sixty-eight (52.7%) subjects had at least 1 serious side effect in the Phase 3 study. The serious side effects investigators thought were related to study drug in this blinded study, include the following: anemia and acquired factor VIII deficiency (a rare but potentially life-threatening bleeding disorder); both events resolved. Sinus Tachycardia (increased heart rate), [resolved and the subject remained in the study]. Increased Liver Enzymes event (GGT increased, 3 alkaline phosphatase, and AST increased) was resolved and the syncope (fainting), the subject who experienced fainting remains in the study.

There is always a chance that an unexpected side effect, including death, may happen to people who take this study drug or any drug. Participants vital status including organ function and immune function will be monitored by the study doctor/staff at least monthly during the study. Participants should tell the study

doctor or medical team about any side effects they are having. The study doctor may be able to give medications to help treat the side effects and prevent them from becoming worse. The study doctor may also choose to stop NEOD001 for a short time or reduce its dose to allow the participant to recover from any side effects.

Amyloid can deposit in vital organs, such as your heart, kidney, liver, spleen. The amyloid in organs can cause them to not function as well as they should. Though NEOD001 is being investigated for its potential to stop or even reverse your organ dysfunction, it is possible that it could cause worsening of organ function when the drug targets the amyloid already deposited in organs. Participants organ function will be monitored closely with blood and urine tests and physical examinations throughout the study.

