#### Appendix 4 Modified Organ Response and Progression Criteria

Organ	Response	Progression
Heart	NT-proBNP response (>30% and >300 ng/L decrease in subjects with baseline NT-proBNP 2650 ng/L) or NYHA class response (2 class decrease in subjects with baseline NYHA class 3 or 4)	NT-proBNP progression (>30% and >300 ng/L increase)
Renal	>30% decrease in proteinuria or drop of proteinuria below 0.5 g/24 hours in the absence of renal progression	>25% decrease in eGFR

Abbreviations: eGFR = estimated glomerular filtration rate; NT-proBNP = N-terminal pro B-type natriuretic peptide; NYHA = New York Heart Association.

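### Section 7.4.3 leaves each site to decide whether non-serious, non-renal organ worsening is recorded as an adverse event, and no by-arm summary of it is prespecified

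*Combined protocol and SAP*

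**What the plan says.** Section 7.4.3 starts from a wide definition: "Disease progression (including progression of hematologic condition and/or organ dysfunction of AL amyloidosis, and death due to disease progression". Progression so defined "is generally recorded as part of the efficacy evaluation and should not be reported as a specific AE or SAE term". One positive instruction follows: "When an AE resulting from disease progression meets the requirements to be considered serious, the SAE verbatim term should be reported as the diagnosis". The illustration given is a pleural effusion. There is no matching instruction for events that are not serious.

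Section 7.1 gives "Exacerbations of the underlying disease (indication" as an example of an adverse event. It also lists new abnormalities of laboratory, physiological or examination findings when clinically significant, and it requires all adverse events on the eCRF whatever their relation to study drug. Section 6.5.1.3 makes clinically significant deterioration on physical examination an adverse event.

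Section 10 names heart, kidney, liver and spleen as organs where amyloid may lie, and says of NEOD001 that "it is possible that it could cause worsening of organ function when the drug targets the amyloid already deposited in organs".

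Appendix 4 defines cardiac worsening as "NT-proBNP progression (>30% and >300 ng/L increase". Section 8.4 assesses safety from vital signs, duration of therapy, "routine laboratory assessments, frequency and severity of AEs as assessed by CTCAE grade".

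**The concern.** Keeping progression out of adverse event reporting is defensible when an efficacy endpoint counts the same events. Here that holds for the kidney and not for the heart, liver or spleen.

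The gap matters because of the harm named in section 10. In a single patient, organ worsening caused by the drug and organ worsening caused by the disease cannot readily be told apart. A comparison between randomised arms can separate them, but only if events are recorded whatever the investigator believes caused them. A rule that turns on attribution to disease works against this. Section 7.3 pulls the same way, since a typical disease-related event is one of its grounds for a rating of not related.

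At stake is the secondary endpoint of safety and tolerability. The monitoring committee's review under section 7.4.5 also depends on what sites enter.

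**Working it through.** No figure in the plan bears on this point, so the check sets the sections side by side.

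**1. Does the efficacy evaluation capture non-renal organ progression?** The primary endpoint (section 3.2.1) is "Confirmed renal response rate after 12 months of treatment with NEOD001 or placebo". The secondary endpoints in section 3.2.2 are:
- measured GFR at entry;
- times to CKD 4 or 5, to low eGFR or dialysis, to doubling of creatinine, and to a 40% fall in eGFR;
- renal response and progression at 26 months;
- safety and tolerability;
- all-cause mortality at 26 months.

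Every organ-specific item is renal. Sections 6.5.2 and 8.3 add no non-renal organ endpoint. Sections 2 and 6.5.2.1 cite Appendix 4 for renal response only, so its heart row is never used.

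**2. What would a site enter?**

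| Event | Site following 7.4.3 literally | Site following 7.1 and 6.5.1.3 |
|---|---|---|
| Serious organ worsening | Diagnosis entered | Diagnosis entered |
| Non-serious, renal | Possibly no adverse event; renal endpoints register it if a threshold is crossed | Adverse event if clinically significant |
| Non-serious, cardiac or other organ | Possibly no adverse event, and no efficacy endpoint | Adverse event if clinically significant |

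The columns differ in the last two rows. Only in the last row is there no efficacy endpoint to fall back on.

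**3. Does the safety analysis close the gap?** Section 6.5.1.1 lists cardiac biomarkers among the safety laboratory tests. Section 8.4 mentions routine laboratory assessments without naming NT-proBNP and commits to no count of patients with organ progression in each arm.

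**4. Are the data there?** Table 1 schedules NT-proBNP after baseline at months 3, 6, 9 and 12 and at the initial and confirmatory EOS visits: 4 + 2 = 6 points. Section 6.1.2.2 lists the test for months 2 to 12 without restricting the months, so six is the smaller reading.

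**5. Illustration (hypothetical patient).** NT-proBNP rises from 700 to 1,400 ng/L without admission to hospital.
- Absolute rise: 1,400 − 700 = 700 ng/L, above 300.
- Relative rise: 700/700 = 100%, above 30%.

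Both parts of the Appendix 4 criterion are met. Under section 7.1 this is an adverse event if judged clinically significant. Under a literal reading of 7.4.3 it may not be entered, and no planned table is certain to show it as progression.

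**6. Effect on the comparison.** Let true rates of such events be p1 and p0, and let sites fail to record a fraction f in each arm (equal fractions are plausible because sites are blinded). The recorded difference is (1 − f)p1 − (1 − f)p0 = (1 − f)(p1 − p0). Under-recording shrinks any true excess by the factor 1 − f. The documents give none of f, p1 or p0.

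**The case against.** The strongest reply is that 7.4.3 restricts a term and not an event. It speaks of a specific term, softens the rule with the word generally, and goes on to discuss adverse events that result from progression, which presupposes that they exist. On that reading it agrees with 7.1. Sections 7.1 and 6.5.1.3 already cover the non-serious case, cardiac biomarkers are classed as safety tests, section 8.4 shows adverse events for both treatment groups, and the NT-proBNP values could be tabulated by arm at any time.

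Much of this stands, and it rules out several stronger readings:
- A reader might infer that non-renal worsening is removed from the safety data, or can appear by arm in no table. The documents do not support that. A site following 7.1 would enter the event and section 8.4 would display it, and NT-proBNP may be read as falling within the laboratory summary.
- A reader might infer that every efficacy endpoint is renal. All-cause mortality is listed too; the statement holds only for organ-specific endpoints.
- A reader might size the problem from the phase 1/2 study, where 36 of 69 patients (52%) were cardiac-evaluable. That describes who could be assessed in another trial, not how many worsen. RAIN also admits only patients with NT-proBNP below 1,800 pg/mL.

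The reply does not dispose of the point. The instruction to use the diagnosis, with its example, is tied to serious events, so the literal reading remains reasonable for the rest. Two reasonable readings across 9 centres is the defect. A laboratory summary by group mean would not show how many patients met Appendix 4. The laboratory values can be recovered later, but a clinical event never entered may not be.

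**Conclusion.** The concern holds in a limited form. Sections 7.4.3, 7.1 and 6.5.1.3 do not agree on whether non-serious organ worsening is an adverse event. For non-renal organs, the efficacy evaluation to which 7.4.3 defers has no endpoint to receive it. Capture of a harm that the protocol itself names as possible therefore depends on the site's reading, and no by-arm summary is prespecified.

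The size cannot be given, because the documents contain no rate of cardiac or other non-renal organ worsening. The direction can: if recording fails equally in both arms, any true excess on NEOD001 is understated in the adverse event data. This rests on two assumptions: that at least some sites apply 7.4.3 literally, and that blinding keeps the omission similar between arms. The primary renal analysis is unaffected. The change should be made; its weight is moderate, since the conflict concerns a named harm and the remedy is cheap.

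**What to change.** 1. Reconcile section 7.4.3 with sections 7.1 and 6.5.1.3. Keep the bar on the bare term disease progression, and state that clinically significant worsening of organ function, serious or not and whether or not attributed to the disease, is recorded under its diagnosis or laboratory term.

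2. Add to section 8.4 a by-arm table, in the Safety Population, of patients meeting the Appendix 4 heart progression criterion, from the NT-proBNP values already scheduled. State which of the two pre-treatment values (screening or month 1 day 1) is the baseline, and give the number of patients with post-baseline values in each arm, since those who stop early will have fewer.

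The cost is one revised paragraph and one table, with no added procedure or sample. The downside is some extra adverse event entries for events that are truly disease; the by-arm display lets the reader judge them against placebo.
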